7.4.3 Clinical Laboratory Assessments

Blood and urine samples will be collected as per Standard of Care and institutional guidelines and as clinically indicated; only clinically significant values should be reported as AEs.

Laboratory assessments are summarized in Table 2.

Table 2Laboratory Assessments

Hematology	White blood cell count, red blood cell count, hemoglobin, hematocrit, mean corpuscular volume, mean corpuscular hemoglobin, mean corpuscular hemoglobin concentration, platelet count, neutrophils (absolute and percentage), lymphocytes (absolute and percentage), monocytes (absolute and percentage), eosinophils (absolute and percentage), basophils (absolute and percentage)
Biochemistry	Sodium, potassium, blood urea nitrogen, creatinine, alkaline phosphatase, alanine aminotransferase, aspartate aminotransferase, creatine kinase, gamma- glutamyl transferase, lactate dehydrogenase, albumin, calcium, phosphate, glucose, total bilirubin, total protein, cholesterol, triglycerides, uric acid, chloride
Urinalysis	Leukocytes, protein, bilirubin, urobilinogen, ketones, red blood cells, pH, nitrite, specific gravity, glucose, microscopy when indicated by abnormal dipstick results

7.4.4 Vital Signs, Physical Examinations, and Other Assessments

7.4.4.1 Vital Signs

Vital signs will be measured as per Standard of Care and institutional guidelines and as clinically indicated.

7.4.4.2 Physical Examination

Physical examinations will be performed as per Standard of Care and institutional guidelines and as clinically indicated. Symptom directed physical examinations will be performed as clinically indicated at the Investigator's judgment.

7.5 Pharmacokinetics

Not applicable.

7.6 Biomarkers

Not applicable.

7.7 Other Assessments

Not applicable.

8 Statistics

Document No. CC	C O N F I D E N T I A L I N F O R M A T I O N	30/54
	Global Version ID: CCI	

8.2 Randomization

Not applicable.

8.3 Endpoints

8.3.1 Primary Endpoints

• Occurrence of AEs and treatment-related AEs in participants receiving berzosertib, graded according to NCI-CTCAE (Version 4.03).

8.3.2 Secondary Endpoints

Not applicable.

8.4 Analysis Sets

For the purposes of analysis, the following populations are defined:

Enrolled analysis set: All participants who sign informed consent for this study.

Safety analysis set: All participants who receive at least 1 dose of study intervention in this study. Participants will be analyzed according to the actual treatment they receive.

8.5 Description of Statistical Analyses

8.5.1 General Considerations

Continuous measurements will be summarized by means of descriptive statistics (i.e., number of observations (n, both available and missing), mean, standard deviation, minimum, median, maximum), and categorical data will be summarized by means of frequency tables (i.e., count and percentages), if not stated otherwise.

If not otherwise specified, "Baseline" refers to the last available measurement before administration of the first study intervention for each dose group from the VX13-970-002 study, as appropriate.

Depending on the number of participants enrolled, no summary statistics will be provided, and the data will be presented in listings only. Details will be provided in the Integrated Analysis Plan.

8.5.2 Analysis of Primary Endpoints

All safety data summaries will be based on the safety analysis set by dose group as from the VX13-970-002 study.

Adverse events will be coded according to the latest available version of the Medical Dictionary for Regulatory Activities (MedDRA). Severity of AEs will be graded using the NCI-CTCAE

Document No. CC	C O N F I D E N T I A L I N F O R M A T I O N	31/54	
	Global Version ID: CCI		

(Version 4.03) toxicity grades. Adverse events will be summarized by frequency and incidence using MedDRA.

Treatment-emergent adverse events (after transition) are defined as AEs that were reported or worsened after signing the Informed Consent Form of this rollover study up to the Safety Follow Up visit (28 [+7] days after the last administration of berzosertib).

Only TEAEs will be summarized in the tables. All summaries of TEAEs will be presented by the severity of the AE and relationship to the study intervention. Some rules that will apply to the summarization of AEs are:

- A participant with multiple occurrences of the same AE or continuing AEs will only be counted once
- Only the maximum severity level will be presented in the severity summary
- Only the worst relationship level will be presented in the relationship summary.

Treatment-emergent AEs leading to study intervention modification or permanent discontinuation will be summarized.

Adverse events leading to death, SAEs, dose interruption of the study, or permanent discontinuation of the study intervention, and SAEs will be listed separately. Pretreatment AEs and TEAEs will be listed in individual participant data listings. Unresolved, ongoing AEs reported at the Safety Follow Up visit (28 [+7] days after the last administration of berzosertib) will be listed separately in an individual participant data listing.

Laboratory and vital signs measurements will be summarized by dose group and/or time point using descriptive statistics for observed values and change from baseline values (as appropriate).

Laboratory values outside the normal ranges will be identified in individual data listings. Shift from baseline according to normal range criteria may also be presented if deemed appropriate.

All clinical laboratory data will be stored in the database in the units in which they are reported and using the laboratory reference ranges as well as in the International System of Units. Participant listings and summary statistics at each assessment time will be presented using the International System of Units.

8.6 **Interim and Additional Planned Analyses**

Not applicable.

9 **Ethical and Regulatory Aspects**

9.1 **Responsibilities of the Investigator**

The Investigator is responsible for the conduct of the study at the site and will ensure that the study is performed in accordance with this protocol, the ethical principles outlined in the Declaration of

Document No. CC	C O N F I D E N T I A L I N F O R M A T I O N	32/54	
	Global Version ID: CCI		

Helsinki, ICH GCP, and any other applicable regulations. The Investigator must ensure that only participants who have given informed consent are enrolled in the study.

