• Is otherwise considered to be medically important. (Note: Important medical events that may not result in death, be life-threatening, or require hospitalization may be considered as SAEs when, based upon appropriate medical judgment, they may jeopardize the participant or may require medical or surgical intervention to prevent one of the outcomes listed above. Examples of such events include allergic bronchospasm requiring intensive treatment in an emergency room or at home, blood dyscrasias or convulsions that do not result in inpatient hospitalization, or the development of drug dependency or drug abuse).

In this clinical study, any late spontaneous abortion, fetal death in utero, ectopic pregnancy, chronic fetal distress, stillbirth, neonatal death, or prematurity-related complication more than is typical for prematurity should be considered as an SAE (see Section 7.4.2).

For the purposes of reporting, any suspected transmission of an infectious agent via a study intervention is also considered an SAE, as described in Section 7.4.1.4.

Events that Do Not Meet the Definition of an SAE

Elective hospitalizations to administer, or to simplify study treatment or study procedures (e.g., an overnight stay to facilitate chemotherapy and related hydration therapy application) are not considered SAEs. However, all events leading to unplanned hospitalizations or unplanned prolongation of an elective hospitalization (e.g., undesirable effects of any administered treatment) must be documented and reported as SAEs.

Events Not to Be Considered as AEs/SAEs

Medical conditions present at the initial study visit that do not worsen in severity or frequency during the study are defined as Baseline Medical Conditions and are not to be considered AEs.

AE/SAEs Observed in Association with Disease Progression

Progression of the disease/disorder being studied assessed by measurement of lesions on radiographs or other methods as well as associated clinical signs or symptoms (including laboratory abnormalities) should not be reported as an (S)AE, unless the participant's general condition is more severe than expected for the participant's condition and/or unless the outcome is fatal within the adverse event reporting period (as defined in Section 7.4.1.3).

Adverse Events of Special Interest

No adverse events of special interest have been identified.

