7.4.1.2 Methods of Recording and Assessing Adverse Events

At each study visit, the participant will be queried on changes in his or her condition. During the reporting period, any unfavorable changes in the participant's condition will be recorded as AEs, whether reported by the participant or observed by the Investigator. Adverse events that are ongoing during transition from the VX13-970-002 study will be recorded at enrollment to ensure the outcome and end date of the AE are captured.

Document No. CC	C O N F I D E N T I A L I N F O R M A T I O N	26/54
()	Global Version ID: CC	

Complete, accurate and consistent data on all AEs experienced for the duration of the reporting period (defined below) will be reported on an ongoing basis in the appropriate section of the eCRF. All SAEs must be additionally documented and reported using the appropriate Report Form as described in Section 7.4.1.4.

It is important that each AE report include a description of the event, its duration, onset and resolution dates (and also onset and resolution times when it is important to assess the time of AE onset relative to the recorded study intervention administration time), its severity, its causal relationship with the study intervention, any other potential causal factors, any treatment given or other action taken, including dose modification or discontinuation of the study intervention, and its outcome. In addition, serious cases should be identified and the appropriate seriousness criteria documented.

Specific guidance can be found in the eCRF Completion and Monitoring Conventions provided by the Sponsor.

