9.2 Participant Information and Informed Consent

An unconditional prerequisite for each participant prior to participation in the study is written informed consent, which must be given before any study-related activities are carried out. Adequate information must therefore be given to the participant by the Investigator or an appropriate designee (if local regulations permit) before informed consent is obtained.

A participant information sheet must be prepared in the local language in accordance with ICH GCP and will be provided by the Sponsor for the purpose of obtaining informed consent. In addition to providing this written information to a potential participant, the Investigator or a designate will inform the participant verbally of all pertinent aspects of the study, using language chosen so that the information can be fully and readily understood by laypersons. The participant will be given sufficient time to read the information and the opportunity to ask questions and to request additional information and clarification.

If permitted by national regulations, a person other than the Investigator may inform the participant about the study and sign the Informed Consent Form (ICF), as above.

After the information is provided by the Investigator, the ICF must be signed and dated by the participant and the Investigator.

The signed and dated declaration of informed consent will remain at the Investigator's site, and must be safely archived so that the forms can be retrieved at any time for monitoring, auditing and inspection purposes. A copy of the signed and dated information and ICF should be provided to the participant prior to participation.

Whenever important new information becomes available that may be relevant to informed consent, the Investigator will revise the participant information sheet and any other written information to be provided to the participants and submit them to the IEC/IRB for review and opinion. Using the approved revised participant information sheet and other written information, The Investigator will explain the changes to the previous version to each study participant and obtain new written consent for continued participation in the study. The participant will be given sufficient time to read the information and the opportunity to ask questions and to request additional information and clarification about the changes.

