# 7 Changes to the Planned Analyses in the Clinical Trial Protocol

Due to the small number of subjects on the study, no statistical analysis will be conducted, and the data will be presented in listings only.

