## 9 General Specifications for Data Analyses

All data will be listed as collected, and no derived datasets will be produced. All listings will be based upon the Study Data Tabulation Model (SDTM) datasets. Subjects will be listed according to the cohort in which they were continued from the previous study.

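### Does defining TEAEs by reporting rather than onset misclassify adverse events carried over from VX13-970-002?

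*Protocol*

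**What the plan says.** Protocol Section 8.5.2 states of TEAEs that they "are defined as AEs that were reported or worsened after signing the Informed Consent Form of this rollover study". The window closes at the Safety Follow Up visit. The section restricts summary tables to TEAEs and adds: "Pretreatment AEs and TEAEs will be listed in individual participant data listings". It does not define the pretreatment category.

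Three other protocol sections bear on an event that began in the parent study:

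- Section 7.4.1.2: "Adverse events that are ongoing during transition from the VX13-970-002 study will be recorded at enrollment". The stated aim is to capture outcome and end date. The same section requires onset and resolution dates for every AE.
- Section 7.4.1.1, on conditions already in place at the first visit: those which "do not worsen in severity or frequency during the study are defined as Baseline Medical Conditions and are not to be considered AEs".
- Section 9.2: written consent is a prerequisite, "which must be given before any study-related activities are carried out".

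On output, Protocol Section 8.5.1 provides that, depending on enrollment, "no summary statistics will be provided, and the data will be presented in listings only", and leaves details to the IAP. IAP Section 7 settles the matter: "no statistical analysis will be conducted, and the data will be presented in listings only". IAP Section 9 adds: "All data will be listed as collected, and no derived datasets will be produced". IAP Section 15.1 plans a listing of all AEs and a separate SAE listing. IAP Section 12 marks concomitant medications that were ongoing at transition; Section 15.1 describes no such mark for AEs.

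**The concern.** In a rollover study the participant arrives already on drug and may bring unresolved events. A TEAE definition should separate those from events that arise or worsen after the move. This one turns on when an event was reported. Because consent comes before any recording, every carried-over event entered at enrollment is, read literally, reported after consent and so treatment-emergent. The Baseline Medical Conditions rule appears to say the opposite, namely that an unworsened pre-existing condition is not an AE. It neither excepts nor cross-refers to Section 7.4.1.2.

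AE occurrence is the only endpoint, so its definition deserves care. Two things could go wrong. Old events could be presented as new, inflating the apparent toxicity of continued treatment. Or a site could apply the Baseline Medical Conditions rule and leave a carried-over event off the eCRF, which no listing could later repair.

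**Working it through.** The plan states no figure to reproduce, since the study has no sample size calculation and no hypothesis test. The check takes one AE with onset in VX13-970-002, ongoing and unworsened at transition, and follows it through each rule.

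| Source | Question it answers | Result for this AE |
|---|---|---|
| Protocol 7.4.1.2 | Is it captured? | Yes, recorded at enrollment |
| Protocol 7.4.1.1 | Is it an AE? | No, if the rule extends to carried-over AEs |
| Protocol 8.5.2, literal | Is it a TEAE? | Yes, reported after consent |
| Protocol 8.5.2, onset sense | Is it a TEAE? | No, onset before consent and no worsening |
| IAP 15.1 | Is it listed? | Yes, if on the eCRF |

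**Are these three incompatible statuses?** No. TEAEs are a subset of recorded AEs, so the first and third rows can both hold. The only real tension is between 7.4.1.2 and 7.4.1.1. The former names the parent study, addresses exactly this event and gives its reason. The latter is a general rule about medical conditions and does not say whether its initial visit belongs to the parent or the rollover study. The specific rule governs capture.

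**Which reading of 8.5.2 fits the rest of that section?** Under Section 7.4.1.3 the AE reporting period opens at ICF signature, so every AE recorded in this study is recorded after consent. On the literal reading:

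- every recorded AE in the window is a TEAE;
- the alternative limb, worsening, adds nothing for carried-over AEs, which already qualify by being recorded;
- the pretreatment category has no members.

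If the test is onset or worsening after consent, the worsening limb covers carried-over events that deteriorate, and the pretreatment category can hold those that do not. Only the second reading gives each part of 8.5.2 something to do.

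**What would the difference be in counts?** Let m be the number of AEs that are new or worsened after consent, and k the number of unworsened carried-over AEs. Neither is in the documents.

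- Literal reading: TEAE count = m + k.
- Onset reading: TEAE count = m.
- Difference = (m + k) − m = k.

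With k assumed to be 0, 1, 2 or 3, the difference is 0, 1, 2 or 3 labels. The extreme case for one participant is m = 0 and k ≥ 1: any TEAE would be 1/1 on the literal reading and 0/1 on the other.

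**Does any planned output show that difference?**

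- Summary tables using the TEAE definition: 0 (IAP Section 7).
- Derived datasets that could carry a TEAE flag: 0 (IAP Section 9).
- AE listings: 2 (IAP Section 15.1). Neither is described as selecting on TEAE status.

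The listing content is therefore the same under both readings. A reader can compare each event's onset date (required by Section 7.4.1.2) with the consent date (kept in the participant file under Section 10.2). Protocol Section 3 describes one participant from Part A1 as having transferred, so this can be done by eye.

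**The case for a change.** The strongest case for a change is that a listings-only plan does not fully dispose of the point. Section 7.4 bases the safety assessment on TEAEs, and 8.5.2 draws the line between pretreatment AEs and TEAEs for listings, the one output type that survives. Section 8.5.1 defers details to the IAP, which supplies no TEAE rule and flags ongoing status for medications but not for AEs. Capture comes before any listing. The repair would be a few words and one flag, with no new data, and Section 3.1 allows participants to be added later.

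Part of this stands. The definition would read better with an onset condition, the pretreatment category is undefined, and a cross-reference between 7.4.1.1 and 7.4.1.2 would help. An ongoing-at-transition mark on AEs would be convenient. Calling unworsened carried-over events pretreatment would not be an improvement, however, because they may have begun on berzosertib in the parent study.

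The rest does not carry. The capture risk requires a site to prefer a general rule over one written for this situation. The missing flag withholds nothing that the dates do not already give. Added participants are remote: Section 3 describes VX13-970-002 as completed, Section 5.3 limits entry to participants ongoing in it, and Section 3.1 makes any addition subject to an amendment, when the wording could be revised. Low cost alone is no reason to amend a plan when no result depends on it.

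**Conclusion.** The wording of 8.5.2 is imprecise, but no change to the plan is needed. An analyst would fill the gap sensibly by treating events with onset before consent and no worsening as carried over, which is also the reading that makes 8.5.2 coherent.

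The effect on planned results is nil: 0 summary tables, and 2 AE listings whose content does not depend on TEAE status. The largest conceivable effect is k extra labels, with k unknown, and it would appear only if the TEAE summaries in 8.5.2 were produced after all, contrary to IAP Section 7.

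This rests on three assumptions: that the study stays at the one transferred participant described, that the listings-only decision stands, and that the site records carried-over events with their onset dates as 7.4.1.2 requires. The eCRF completion conventions mentioned in 7.4.1.2 are not among the documents, so how a worsening event is entered could not be checked. If TEAE tables were reinstated, the definition should be revisited first.

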Planned study and treatment duration per participant: Participants can continue treatment until disease progression or unacceptable toxicity is reported. The End of Study is defined by the completion of a Safety Follow Up visit to be scheduled 28 (+7) days after the last administration of berzosertib.

Statistical methods:

CCI

Safety:

All safety data summaries will be based on the safety analysis set.

Adverse events will be coded according to the latest available version of the Medical Dictionary for Regulatory Activities (MedDRA). Severity of AEs will be graded using the NCI-CTCAE (Version 4.03) toxicity grades. Adverse events will be summarized by frequency and incidence using MedDRA.

Safety data measurements will be summarized by dose group and/or time point using descriptive statistics for observed values and change from baseline values (as appropriate).

Table 1Schedule of Assessments for Participants Transitioned from Part A1: Single Agent Therapy once weekly

		Treatment Cycle (21 days)		Follow Up ^b	
Event/Assessment ^a	Enrollment	Day 1	Day 8	Day 15	28 (+7) days after last administration
Safety Assessment					
Informed consent	Х				
Demographic and other Baseline Characteristics	Х				
Concomitant medication/AEs	Continuous from signing Informed Consent Form through Safety Follow Up visit				
Study Intervention Administration					
Berzosertib dosing		Х	Х	Х	

AE = Adverse event

a Physical examination, weight, vital signs, serum chemistry, hematology and urinalysis will be measured as per Standard of Care and institutional guidelines and as clinically indicated; only clinically significant values should be reported as AEs.

b Follow Up will include a Safety Follow Up Visit to be scheduled 28 (+7) days following the last administration of berzosertib.

Document No.	CCI
Object No CC	

Global Version ID: CCI

2 Sponsor, Investigators and Study Administrative Structure

This clinical study will be sponsored by Merck KGaA (Darmstadt, Germany).

The number and nature of study sites will be determined by the actual need. It is expected that participants from a single site in the UK will enter this Safety Follow Up study. Further sites and countries may be added via amendment(s) to this protocol in the future if new demand for participants transitioning into this transition rollover study emerges.

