Appendix V: Protocol Amendment History

The information for the current amendment is on the title page.

The following information provides a high-level summary of previous amendments with the most recent amendment listed first.

Section # and Name	Description of Change	Brief Rationale
Synopsis Table 1 Section 7.4.3 Clinical Laboratory Assessment Section 7.4.4.1 Vital signs Section 7.4.4.2 Physical Examination	Laboratory assessments (serum chemistry, hematology, and urinalysis), vital sign measurements, and physical examination will be only performed according to Standard of Care and institutional guidelines and as clinically indicated; only clinically significant changes will be recorded as adverse events (AEs).	To reduce the study assessments for the participant and clinical site, leveraging them according to the clinical site Standard of Care. The study requires any clinically significant values to be collected as AEs to ensure patient's safety throughout the study treatment.
Synopsis	Planned study period changed to" estimated 5 years"	For clarity.
Synopsis Section 8.3.1 Primary Endpoints	Primary endpoint updated to "Occurrence of adverse events (AEs) and treatment-related AEs in participants receiving berzosertib, graded according to the National Cancer Institute Common Terminology Criteria for AEs (NCI-CTCAE) (Version 4.03)"	To align with current Merck KGaA endpoint library.
Table 2	Removed Table 2 (VX13-970-002 Part B2) SoA.	Since VX13-970-002 study was completed and no participants from Part B2 were transitioned to this study.
Section 3 Background Information Section 3.1 Study Rationale	Description of VX13-970-002 study was updated and description of VX12-970-001 study was deleted.	Since VX13-970-002 study was completed and no participants were transitioned to this study from Study VX12-970-001.
Figure 1	Updated and simplified Figure 1	For clarity.
Section 5.7 Definition of End of Study	Added the statement "The Sponsor may terminate the study at any time once access to berzosertib for participants still benefiting is provisioned via expanded access, marketed product or another mechanism of access as appropriate".	For flexibility and clarity.

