Section 6.2 Dosage and Administration Section 6.4 Noninvestigational Medicinal Products to be Used(deleted) Section 6.4.1 Permitted Medicines	Text regarding infusion of berzosertib after chemotherapy (carboplatin and paclitaxel) removed	Since participant not receiving any chemotherapy agents (paclitaxel and carboplatin).

Amendment 2 (17 November 2020)

Section # and Name	Description of Change	Brief Rationale
Section 7.4 Assessment of Safety	Added the statement "Physical examination, weight, vital signs, serum chemistry, hematology and urinalysis will be measured as per Standard of Care and institutional guidelines and as clinically indicated; only clinically significant values should be reported as AEs. A clinically significant value is a result that a clinician would consider to be medically meaningful. Clinically significant values may be more severe than values expected for the participant's condition, age, and gender".	For clarity.
Section 7.4.1 Adverse Events	Section updated and text added to specify that "In this clinical study, any late spontaneous abortion, fetal death in utero, ectopic pregnancy, chronic fetal distress, stillbirth, neonatal death, or prematurity- related complication more than is typical for prematurity should be considered as an SAE."	To align with current Merck KGaA standard.
Section 7.4.1.4 Procedure for Reporting Serious Adverse Events	Specified that serious adverse events to be reported using Electronic Data Capture (EDC) and paper reports required only in case of EDC system failure.	This study will use electronic Case Report Forms.
Section 8.5.1 General Considerations	Specified that depending on the number of participants enrolled, no summary statistics will be provided and the data will be presented in listings only.	Only one participant was enrolled in this study to date. All other participants completed berzosertib study intervention within the initial study protocol.
Section 10.1 Case Report Form Handling	Removed text about paper Case Report Forms.	This study will use electronic Case Report Forms.
Section 10.2 Source Data and Participant Files	Added a clarification statement regarding when printing files is not necessary.	To add flexibility to study data management.
Appendix I Contraception	Contraception information updated.	To align with current Merck KGaA standard.

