Appendix III Vertex VX13-970-002 Clinical Study Protocol	Removed previously appended Vertex protocol.	To align with Merck standard not to append a protocol with standalone documents.
Appendix IV Protocol Amendment History	The protocol amendment history information was moved to the front of the document.	To align with current Merck standards and style of reporting.
Throughout	Minor editorial and document formatting revisions	Minor; therefore, not summarized.

Amendment 1 (18 September 2017)

Section # and Name

Description of Change

Brief Rationale

Table 1 header and vital signs/footnote

Deleted 28 days in treatment cycle and added vital signs at Day 15.

For clarification and to update to company standards for vital sign measurements.

Document No. 0900babe815bc205v1.0 Object No. 0900babe815c193f

CONFIDENTIAL INFORMATION Global Version ID: 78691_1399695_1750929

53/54

Section # and Name	Description of Change	Brief Rationale
Table 2 (VX13-970-002 Part B2) footnote	Vital sign measurements clarified in table footnote.	To update to company standards for vital sign measurements.
Table 2 (VX13-970-002 Part B2) footnote	The following footnote was added:	To provide for a plan in case of combination tolerability issues.
	"The participants who are not able to tolerate combination therapy due to toxicity associated with carboplatin and/or paclitaxel and continue on single agent M6620 should be assessed according to Schedule of Assessments for Participants Transitioned from Part A1: Single Agent Therapy once weekly (see Table 1)"	
Section 5.1 Overall Study Design and Plan	Added sentence specifying that participants who transferred from combination treatment to M6620 monotherapy before enrollment in this rollover study should continue accordingly in this protocol.	For clarification.
Throughout	Minor editorial and document formatting revisions	Minor; therefore, have not been summarized

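### Do the laboratory and vital-sign listings need changing because the IAP predates the move to Standard of Care testing?

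*Protocol*

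**What the plan says.** **Testing.** Table 1 of the protocol has rows for consent, demographics, concomitant medication and adverse events, and dosing, but none for laboratory tests or vital signs. Footnote a to Table 1 and section 7.4 say that these, with physical examination and weight, "will be measured as per Standard of Care and institutional guidelines and as clinically indicated; only clinically significant values should be reported as AEs". Sections 7.4.3 and 7.4.4 say the same about when testing is done.

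**Analysis wording in the protocol.** Section 8.5.2 has laboratory and vital-sign measurements "summarized by dose group and/or time point using descriptive statistics for observed values and change from baseline values (as appropriate"); the synopsis has a similar sentence for safety data. The end of 8.5.2 adds "Participant listings and summary statistics at each assessment time will be presented using the International System of Units" and "All clinical laboratory data will be stored in the database in the units in which they are reported". Section 8.5.1 takes baseline from the parent study. It also says that, depending on how many participants enrol, "no summary statistics will be provided, and the data will be presented in listings only", and leaves the details to the IAP.

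**IAP.** The modification history shows v1.0 of 28 January 2019 and nothing later. Section 7 drops statistical analysis in favour of listings because there are few subjects. Section 9 lists data as collected, from the SDTM datasets, without derived datasets. Section 15.2 lists laboratory results with normal ranges and high/low flags, and 15.3 lists vital signs and weights as collected.

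**Dating.** Appendix V is used here only to date the change. It records that laboratory tests, "vital sign measurements, and physical examination will be only performed according to Standard of Care and institutional guidelines and as clinically indicated". Its Amendment 2 entries (17 November 2020) include "Only one participant was enrolled in this study to date". Its Amendment 1 entries (18 September 2017) include "Deleted 28 days in treatment cycle and added vital signs at Day 15".

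**The concern.** Three features together suggest a fault. Section 8.5.2 refers to time points and assessment times that Table 1 no longer sets. The IAP predates the change in testing, and nothing shows that it was revisited. The reported participant had already been enrolled when the change was made, so that person's data may cover both a period with protocol-scheduled assessments and a period of Standard of Care testing.

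The worry is about how the listings are read. Laboratory findings reach the primary endpoint only when they are judged clinically significant and reported as adverse events. If testing became less frequent, a later stretch with few laboratory events could reflect fewer tests rather than better tolerability. Gaps in the listing could also be mistaken for missed assessments. Long-term safety is the study's only objective and listings are its only planned output, so the question deserves a check.

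**Working it through.** No design figure exists to reproduce. The protocol states no sample size, power or event count, and its synopsis says no sample size considerations were made. The check is of dates and of which text governs the output.

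1. **Dates.** From 28 January 2019 (IAP v1.0) to 28 January 2020 is 365 days, and on to 17 November 2020 is 294 days: 365 + 294 = 659 days. In 21-day cycles, 659 / 21 = 31.4. From 18 September 2017 (Amendment 1) to 18 September 2020 is 1,096 days, and on to 17 November 2020 is 60 days: 1,096 + 60 = 1,156 days, and 1,156 / 21 = 55.0 cycles. These are intervals between documents. They do not measure the participant's time under either schedule, because neither the enrolment date nor the date the amendment took effect at the site is given.

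2. **Dating of the change.** In the text as extracted, the Appendix V row on Standard of Care testing stands above the Amendment 2 heading. The section 7.4 row below that heading carries the same statement, so November 2020 is a reasonable date.

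3. **Do the 8.5.2 summaries run?** No. Section 8.5.1 makes them depend on the number enrolled, and IAP 7 decides for listings only. Even if they ran, one participant would give one value per parameter and time. The mean, median, minimum and maximum would all equal that value, and the standard deviation, with divisor n − 1 = 0, would be undefined. The time-point sentence therefore has no effect. It also allows dose group alone and is qualified as applying where appropriate.

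4. **Is change from baseline computed?** No. IAP 9 produces no derived datasets, so the question of how a parent-study baseline would be obtained does not arise.

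5. **Does the reference to assessment times bind the listings to a schedule?** That sentence prescribes the units of presentation. A Standard of Care measurement also has a time at which it was taken, so the sentence can be followed without protocol visits.

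6. **Do the listing rules fail under Standard of Care testing?** Each IAP rule is set against the current protocol:

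| IAP rule | Needs a visit schedule? |
|---|---|
| 9: list data as collected | No |
| 15.1: list all AEs, with a separate SAE listing | No |
| 15.2: list laboratory results with ranges and flags | No |
| 15.3: list vital signs and weights as collected | No |

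7. **Would two kinds of value be mixed?** The documents do not establish this. Appendix V shows that vital signs were once scheduled, and its rationale of reducing study assessments implies the same for laboratory tests, but no earlier laboratory frequency is visible. No text says which Standard of Care results are entered in the eCRF. If they are entered, both kinds could share a listing. If they are not, the listing simply ends. It is also not shown that testing became sparser: the Standard of Care frequency is not given, and Table 1 still has dosing on Days 1, 8 and 15 of each cycle.

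8. **Is a planned result biased?** No analysis of adverse-event frequency over time is planned, and there is no comparator. A reader who wants to relate events to the change has the amendment date in the protocol, and 7.4.1.2 calls for onset and resolution dates for each adverse event.

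**The case for a change.** The strongest case for acting is that alignment is the plan's own standard. IAP 4 says the IAP rests on Section 8 of the protocol and its amendments, and 8.5.1 sends the reader to the IAP for detail. Yet the IAP was not reissued after November 2020, and its endpoint in section 5 lacks the treatment-related events that protocol 8.3.1 now names. A collection date beside a value does not tell the reader when scheduled testing ended. The remedy would be cheap: a reissued IAP, a footnote in three listings and one sentence on eCRF entry. IAP 6 already provides a data review meeting before lock at which it could be made.

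Part of this stands. The IAP does look unrevised, the time-point wording is left over, and the eCRF entry rule is not written in either document. None of it makes a planned output wrong. On format, the protocol moved towards the IAP: Amendment 2 put into 8.5.1 the listings-only approach that IAP 7 had adopted in January 2019. The endpoint difference does not lose data either. Section 7.4.1.2 collects causality for each adverse event, and IAP 15 lists all safety data as collected. The eCRF entry rule can sit in the Manual of Operations, to which protocol 10.1 refers for eCRF handling. A footnote with the amendment date would be a courtesy to readers, and whoever prepares the study report can add it without a change to the plan.

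**Conclusion.** The concern does not call for a change. The leftover wording describes summaries that will not be produced, and the listing rules that do apply work whether or not testing is scheduled. The unstated eCRF entry rule is a matter of operational detail that data managers and analysts can settle sensibly before lock.

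The effect on planned results is nil: one reported participant, listings only, no statistics, and adverse events as the primary endpoint. The 659-day and 1,156-day intervals are correct as date differences but measure no effect on the data.

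This rests on three assumptions. Enrolment stays at or near the one participant reported in the amendment log. Summaries are not reinstated; if participants were added by amendment, as protocol 2 and 3.1 allow, and summaries then returned, the IAP would need revising for that reason. The November 2020 date for the change is right; the log supports it, although the current amendment's own summary is on a title page outside the text reviewed.
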